#### **C.2.4. Measures**

Trial Feasibility will be assessed with several metrics recommended by Leon et al.

##### Aim 2.a. (recruitment and study retention)

- Number of participants screened per month
- Number enrolled per month
- Proportion of screened participants who are eligible to enroll
- Completion rates of follow-up assessments

Aim 2.b. (participant adherence and retention in treatments, provider and peer treatment fidelity)

- Retention rates in both study interventions
- PCBMT facilitator fidelity. PCBMT facilitators will complete a checklist of essential elements after each class. Co-I's [name] or [name] will observe 25% of all classes and independently rate the fidelity assessment piloted in our earlier PCBMT study (Appendix 3). This assessment was developed based on the guidelines published by Borrelli et al. and documents observations on the delivery and enactment of treatment skills.

Aim 2.c. (intervention acceptability) will be measured at post-treatment by 2 measures.

- The *Client Satisfaction Questionnaire (CSQ)* is an 8-item self-report measure with strong psychometric properties: higher scores are related to treatment completion and symptom reduction.
- *Intervention Acceptability* is a self-report measure created for this study to assess participants' reactions to their assigned intervention, including perceived helpfulness of core intervention components, specific symptoms or functional concerns that improved, and if and how the intervention contributed to meeting the participants' personal recovery goals. Retention (# of sessions attended) will also contribute to measuring intervention acceptability.

Aim 2.d.i. (patient functional status) will be measured at baseline, post-treatment and 16 and 24 week follow-up by 3 measures.

- *PTSD Checklist-5 (PCL-5)* is a 20-item self-report measure that asks respondents to rate how much they have been bothered by DSM-5 PTSD symptoms in the past month. We will administer this with the extended assessment of traumatic events to ensure that the symptoms reported are related to an event that meets criteria for a traumatic event. Early psychometric study of the PCL-5 indicates excellent reliability and validity. A cut point of 31 along plus meeting Criterion A will be required for study inclusion to allow Veterans with subthreshold PTSD to participate. The total score will be used to indicate PTSD severity at each time point. Since participants must wait to begin the intervention until enough participants are enrolled to form a group, the PCL-5 will be re-administered if participants do not attend class 1 within one month of their baseline interview.
- *Recovery Assessment Scale (RAS)* is a 24-item self-report measure that will assesses various aspects of recovery from the perspective of the Veteran, with an emphasis on hope and self-determination. It covers 5 domains: personal confidence and hope; willingness to ask for help; goal and success orientation; reliance on others; and no domination by symptoms. It has high reliability and good concurrent validity.
- *Patient Health Questionnaire-9 (PHQ-9)* assesses 9 symptoms of depression on a 4-point scale. Participants who endorse the suicidality item will also be administered the P4 screener which assess past history, plan, probability, and preventive factors for suicide.
- *Health Promoting Lifestyle Profile II*

Hypothesized mediators will be assessed with 2 psychometrically sound measures at each time point.

- *Self-Compassion Scale- Short Form*
- *Five Facet Mindfulness Questionnaire (FFMQ)* is a 39-item scale measuring observing, describing, acting with awareness, non-judging, and non-reactivity.
- *Emotion Regulation Questionnaire (ERQ)* is a 10-item self-report measure designed to assess the use cognitive reappraisal and expressive suppression.

**C.2.5. Intervention Conditions:** The PCBMT and EDU groups will share several structural features: both will be 1) located in primary, 2) co-led by a licensed mental provider (psychologist, clinical social worker, mental health counselor) and a Veteran peer support specialist, 3) consist of four 90-minute weekly sessions, 4) Peers will meet briefly (30 minutes) to guide participants in completing the Personal Health Inventory (PHI) prior to starting their assigned treatment condition. The PHI was developed by the VHA Office of Patient Centered Care and Cultural Transformation and is a commonly used by VHA peers support specialists. The PHI will allow participants to engage in self-reflection regarding what matters most to them in their lives (Appendix 4). This discovery process will inform the identification of personal health goals that align with their values and priorities, and thus ideally increase patient activation and engagement. This process supports the delivery of personalized, proactive, and patient-driven care. Completed PHIs will be shared with the group facilitators to help personalize the intervention. 4) During the meeting with the peers, participants will also watch a video to orient them to their assigned condition. PCBMT participants will watch the 7-minute "What is Mindfulness?" video from the VHA OPCC. EDU participants will watch two 3.5-minute whiteboard videos "What is PTSD?" and "Treatment: Know Your Options" from the VHA National Center for PTSD. 6) Printed instructions for homework will be provided and participants will be asked to submit simple forms during each class that record the type and number of minutes of at home practice completed. For PCBMT this will include time spent in

formal and informal meditation. 7) Peer co-leaders will act as peer-navigators to help participants connect to any additional MH, case management, or medical care needed.

PCBMT is a manualized intervention that is a brief adaptation of MBSR (Table 3, appendix 5). It was developed by Co-I, [name] over the last decade and is regularly delivered to community members. Its delivery to Veterans is described in B.1. PCBMT consists of four 90-minute group classes (360 total minutes of classes). Instruction encompasses sitting meditation, body scan, moving meditation, gentle yoga, and group discussion on topics such as non-judging, patience, trust, non-striving, acceptance, and letting go. Drs. [name] and [name] will provide weekly group supervision for the mental health providers and peers that are delivering PCBMT. The aim of supervision is to strengthen program quality through discussion of how PCBMT is being enacted, processing challenges as they arise, and modeling skillful inquiry. Supervision is also an opportunity for providers and peers to examine their PCBMT teaching and facilitation skills. In addition, the PI will meet with all peers delivering PCBMT for an additional weekly supervision that focuses on peer-specific roles and challenges including completing the Patient Health Inventories and peer treatment navigation. The PI will dedicate the time to meet the on-going educational needs of peers (e.g., additional training in PTSD concerns or treatment options), advise on non-specific treatment factors (e.g., active listening skills), and how best to use their own lived experiences to help participants in their recovery. The PI is currently providing peer supervision for the study described in B.3 and is the clinical supervisor of a peer who delivers non-research services in primary care.

Table 3. Primary Care Brief Mindfulness Training Session-by-Session Content

Group #: Theme	Session Content	Weekly Assignment *
#1: There is more right with you than wrong with you	
 
Introduction (expectations, ground rules)
 
Brief exercise: “The Well” (Why are we here?)
 
What is mindfulness? (foundation, intention & commitment, integrating into daily living)
 
Raisin meditation
 
Body Scan – 20 minutes
 
Brief sit with breath awareness
 
	
 
20 minute body scan daily and mini-sitting on CD
 
Using breath awareness in stressful situations
 
Mindful eating
 
Mindfulness of routine activities
 
Daily log of minutes spent on various mindful activities
 
Readings: “Incline your Mind” by the group facilitator; Chapters 1-3 of “Full Catastrophe Living” (Kabat-Zinn, 1990)
 

#2: Perception and creative responding	
 
Review past week (issues with meditations, seeing change, difficulties)
 
20 minute sitting – breath awareness, physical sensations, sounds
 
Stress reactivity vs. response (using mindfulness to short circuit reaction)
 
Yoga and awareness
 
	
 
Alternate stretching/mini-body scan* with 20 minute sitting
 
Capturing pleasant & unpleasant moments
 
Using the breath to slow things down
 
Awareness of what we take in (substances, sounds, violence)
 
Daily log of minutes spent on various mindful activities
 
Readings: “Thoughts on Thoughts”. “Why Meditate” NY Times articles by [name].
 

#3: Communication, expression of feelings, maintaining one’s center in interpersonal relationships	
 
Brief sitting
 
Review of past week
 
Communication styles, separating fact from story, awareness of emotional reaction, focus on content
 
Mindful listening exercise
 
Introduce Metta meditation
 
	
 
Alternate “Metta” with any other 20 minute meditation
 
Awareness of difficult communications (observing reactivity, using the breath to try to minimize reactivity)
 
Observation of diet (underlying emotions, slowing down)
 
Daily log of minutes spent on various mindful activities
 
Readings: “Cultivating Self-Compassion” and “Mindfulness & Mastery” by [name].
 

#4: Making this practice your own	
 
Yoga followed by body scan
 
Review of past week
 
	
 
Final Reading: “Continue Down the Mindful Path” by [name].
 

 
• Introduce walking meditation
 
• Brief sitting, loving-kindness
 
	
 
• Resources for continued practice.
 

--	---

\* Participants are asked to use the provided 2-minute Chill Out audiorecording at least once daily on all weeks.

EDU is a class designed to provide a supportive environment for learning about PTSD-related issues and to help Veterans determine what recovery strategies will be most helpful for them. Session themes include “Civilian Readjustment and PTSD,” “Trust, Safety, and Healing” and “Treatment Strategies.” This group is currently delivered at the Syracuse site (co-led by a licensed mental health provider and a peer) and a very similar class is delivered at the Canandaigua site. Therefore EDU is an active, PTSD-specific, primary-care based “treatment as usual” comparison group (Appendix 6). These classes were developed locally and no research has been conducted on them. However, psychoeducation for PTSD is often described as an ideal introductory intervention for individuals first entering treatment.

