Primary care patients will be recruited and assessed pre and post intervention and at 16 and 24 week follow-up time points. Each quarter, two months will be spent recruiting and 1 month will be used to conduct the intervention groups. Ideal group size is 6 participants. We anticipate running up three consecutive groups (PCBMT and EDU) at each of the two sites. However, our timeline allows for addition groups as needed. To be eligible, participants must be 1) enrolled in primary care at the Syracuse or Canandaigua VAMC and 2) report significant PTSD symptoms (qualifying criterion A traumatic event plus at least a 31 on the PCL-5). Exclusion criteria are minimized because we seek to include any primary care patients with troubling PTSD symptoms that would normally receive treatment in primary care. Patients will be excluded if they demonstrate symptoms that would not allow them to actively participate in PCBMT: 1) gross cognitive impairment ( $>16$  on the Blessed OMC), 2) suicide attempt or desire to commit suicide in the last month (as measured by P4 screener). To allow the study to isolate the effects of the intervention and ensure patient treatment preferences are honored, patients will be excluded if they 3) have received psychotherapy or change in psychiatric medication outside of VHA primary in the last 2 months, or 4) voice a preference to be directly referred to specialty mental health care. Veterans with depression, anxiety disorders, mild TBI, and alcohol/ substance use disorders will not be excluded, because these problems commonly co-occur with PTSD, and individuals with these conditions have previously benefited from mindfulness training. Patients who receive PC-MHI services will not be excluded, as this is part of the usual primary care services that all Veterans can receive.

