**C.2.3 Phase 2 Procedures:** The baseline session will include informed consent process (Appendix 2) followed by administration of study measures. Participants will be screened for cognitive impairment with the Blessed Orientation Memory and Concentration measure and suicidality with P4 Screener. The P4 Screener assessed past history, plan, probability, and preventive factors and then classifies respondents as minimal, lower or higher risk for suicide. At the baseline assessment, higher risk participants will be connected to VHA Suicide Prevention Services prior to continuing them in the study. In addition to assessing primary outcomes and patient safety, we plan to test the feasibility of measuring concerns that commonly co-occur with PTSD (depression, insomnia, pain, and alcohol/substance misuse) and potential mediators of the relationship between receiving mindfulness training and changes in PTSD symptoms and psychosocial functioning (mindfulness and emotion regulation skills). Pilot data in this area will help us plan for a future full-scale investigation of potential mediators. Post-treatment assessment will occur upon completion of the assigned intervention. We will re-assess participants at two follow-up points: 16 weeks and 24 weeks post-baseline. This will allow the opportunity to test the feasibility of retaining participants over time so that in the full-scale future trial we can test if any changes observed post-treatment are maintained over time. Given that an aim of this line of research is for PCBMT to serve as a bridge to other more intensive PTSD treatments, within the full-scaled trial, data from the 24 week follow-up will also allow the ability to measure changes associated with any new treatments initiated post study treatment. All research assessments will be administered by research staff blinded to randomization outcome. Participants will be reimbursed \$25 per assessment (\$100 total). Randomization will be stratified based on baseline PCL-5 scores (31-40 vs.  $>40$ ) to equate groups at baseline.

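### When class 1 falls more than one month after baseline, the PCL-5 is repeated but no suicide-risk measure is; adding the P4 Screener to that repeat is a cheap safety improvement

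*Combined protocol and SAP*

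**What the plan says.** Four parts of the protocol bear on this.

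- **Eligibility (C.2.1).** Exclusion 2 is "suicide attempt or desire to commit suicide in the last month (as measured by P4 screener". It is listed among "symptoms that would not allow them to actively participate in PCBMT".
- **Baseline (C.2.3).** The P4 Screener is given at the baseline session. The stated action is: "At the baseline assessment, higher risk participants will be connected to VHA Suicide Prevention Services prior to continuing them in the study". The same section adds: "Post-treatment assessment will occur upon completion of the assigned intervention".
- **Waiting period (C.2.4, PCL-5 entry).** The protocol notes that "participants must wait to begin the intervention until enough participants are enrolled to form a group", and for that reason "the PCL-5 will be re-administered if participants do not attend class 1 within one month of their baseline interview". It does not say what the repeated score is used for.
- **Later checks (C.2.4, Aim 2.d.i).** The block that lists the PHQ-9 "will be measured at baseline, post-treatment and 16 and 24 week follow-up by 3 measures". The PHQ-9 entry says: "Participants who endorse the suicidality item will also be administered the P4 screener". The heading counts three measures and four are listed, but C.3 (2.d.i) reports depression at each time point, so I take the PHQ-9 to be given at all four.

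**The concern.** The protocol treats recent suicidality as relevant to taking part in the classes. It also expects some participants to start more than a month after they were screened for it, and plans a repeat measurement for exactly those participants. The P4 is not part of that repeat. For a delayed participant, no suicide-risk measure is specified between the baseline P4 and the post-treatment PHQ-9, so the wait and all four classes go by without one.

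What is at stake is participant safety. A participant whose risk rose during the wait could miss the connection to services that the protocol requires for higher-risk participants at baseline. No estimate, sample size or analysis is affected.

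**Working it through.** **Inputs**

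- Cycle: two months recruiting, then one month of groups, each quarter (C.2.1).
- Classes: four, weekly (C.2.5), so class 4 comes 3 × 7 = 21 days after class 1.
- Enrolment: 5 per month, 60 in one year (C.2.2).
- My convention: one month = 30.44 days.
- My assumptions where stated: even accrual, and class 1 directly after the recruiting block.

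**The plan's own figure.** 5 × 12 = 60, which reproduces the target. With recruiting in only 8 months of the year (two per quarter), 5 × 8 = 40. The two schedule statements do not fit together, so I give a share per recruiting block and no count out of 60.

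**Which checks are specified, and when**

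| Time | Suicide-risk measure specified |
|---|---|
| Baseline | P4 for everyone; PHQ-9 item |
| Class 1 more than one month after baseline | None (PCL-5 only) |
| Classes 1 to 4 | None |
| Post-treatment | PHQ-9 item, then P4 if endorsed |
| 16 and 24 weeks | PHQ-9 item, then P4 if endorsed |

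**Age of the baseline P4 at class 1, delayed participants**

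- Shortest: just over one month, 30.44 days.
- Longest, with class 1 directly after the block: 2 × 30.44 = 60.88 days.
- Latest class 1 that still fits four weekly classes into the group month: 30.44 − 21 = 9.44 days into that month. The longest wait is then 60.88 + 9.44 = 70.3 days.

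The range is therefore about 30 to 61 days, and up to about 70.

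**Is post-treatment really the next check?** The longest time from baseline to class 4 is 70.3 + 21 = 91.3 days. Week 16 is day 112. So post-treatment comes first in every case under this cycle.

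**Share waiting more than one month**

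- With even accrual over L months and class 1 directly after: (L − 1)/L. For L = 2 this is 1/2 = 50%. At 5 per month that is 5 of the 10 enrolled in a block; the share does not depend on the rate.
- With the latest class 1: (60.88 − (30.44 − 9.44))/60.88 = 39.88/60.88 = 66%.

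Uneven accrual would move these figures either way. The documents give no distribution of waiting times, so I put no range on that.

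**The case against.** **Eligibility is settled once, at enrolment.** A reader might infer that eligibility lapses after a month and that the plan therefore contradicts itself. The documents do not support this. The one-month window is the look-back of an entry criterion, and nothing says it must be met again before class 1. The other time-limited exclusion in C.2.1 (psychotherapy or medication change in the last two months) is not re-checked either. This objection stands.

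**The PCL-5 repeat may have nothing to do with screening.** It sits in an outcome-measure entry, right after the statement that the total score indicates severity at each time point. A refreshed pre-treatment score is a natural reading. This also stands. What remains is that a repeat administration is already planned at the right moment and the P4 could be added to it.

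**Higher risk does not bar participation.** A reader might infer that a delayed participant with raised risk would be someone the protocol keeps out. C.2.3 lets higher-risk participants continue once they are connected to services. What could be missed is that connection.

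**Participants are seen.** A peer meets each of them before treatment, a licensed provider co-leads every class, and peers help with access to further care (C.2.5). It would be wrong to say that risk goes unobserved. None of these contacts is described as a suicide screen, though, so they narrow the gap without closing it.

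**The gap can be made to look larger than it is.** Counting from baseline to class 4 gives 30.44 + 21 = 51 to 60.88 + 21 = 82 days, but 21 of those days are the classes. Someone who waits just under a month reaches class 4 after nearly 51 days too, and the fix does not touch that case. One month is a convenient trigger because the repeat is already scheduled then; it is not a safety threshold.

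**The procedure may exist elsewhere.** Section B and the appendices are cited but not in the document, so the absence can be claimed only for the text available.

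**Conclusion.** The point holds as a cheap improvement. In the text available, a participant who starts class 1 more than one month after baseline has the PCL-5 repeated and no suicide-risk measure. The last specified P4 is then about 30 to 61 days old under the two-month recruiting cycle (up to about 70 with the latest class 1), and the next specified check is the post-treatment PHQ-9.

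That the gap exists needs no accrual assumption, since C.2.4 itself provides for a delayed start. Its length rests on the cycle in C.2.1. The share affected, about 50%, rests on even accrual and on class 1 following directly after recruiting.

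A reader might go further and infer that the trial leaves suicide risk unmonitored, or that harm is likely. The first is wrong, because the PHQ-9 item leads to a P4 at each scheduled assessment. On the second, the documents give no rate of new suicidality during the wait, and I assume none.

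**What to change.** In the PCL-5 entry of C.2.4, replace the repeat clause with wording such as:

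> If class 1 has not been attended by one month after baseline, the PCL-5 and the P4 Screener are both repeated before class 1. Anyone classed as higher risk, or reporting a suicide attempt or desire in the last month, is connected to VHA Suicide Prevention Services before attending class 1. Anyone already randomized keeps the allocation and all follow-up, and is analyzed as randomized.

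The last sentence keeps the safety step from removing randomized participants from the comparison.

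The cost is a few sentences of protocol text and one short extra screen per delayed participant, using an instrument already in the study. The few who screen positive may start slightly later. Sample size and analysis do not change. If section B or an appendix already contains such a procedure, a cross-reference in C.2.4 is enough.

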### C.3 Analysis Plan

Aim 1: Gather VHA mental health treatment provider and peer feedback to adapt PCBMT. Co-I [name] will oversee Aim 1 analyses using a Rapid Assessment Process (RAP). This approach is ideal when data needs to be collected and analyzed in one year or less, when only key informants will be interviewed, and when analyses will be deductive. The PI and project coordinator will conduct interviews together with the PI primarily asking questions and the coordinator typing detailed field notes to document responses. A template will be created with a domain name for each interview question (e.g., activating patients, peer roles). The PI, coordinator, and [name] will review the first few sets of field notes collaboratively and summarize content into the domains on the template. After consistency is reached, coders will review the remaining field notes ( $\approx 7$ ) independently. Led by [name], coders will then meet again to analyze summaries and identify suggestions for revisions or aspects seen as helpful that should be maintained within each domain. The PI and Co-Is [name], [name] and [name] will then meet and collectively decide how to modify the protocol. Modifications will only be made if the resulting PCBMT protocol is: 1) feasible to deliver in VHA primary care and 2) stays true to the core mindfulness components. Modifications will be prioritized that are expected to 3) help Veterans develop skills for PTSD symptom management, 4) increase the training’s patient-centeredness, and 5) will affect multiple qualitative domains.

Aim 2: Conduct a pilot RCT (N=60 randomized, n=48 completers) comparing PCBMT to EDU.

**2a.** As this trial will provide us with feasibility information for a larger trial, we will describe the number of participants screened and enrolled per month, proportion of screened participants who are eligible to enroll, completion rates of follow-up assessments, retention rates in study conditions, and the rate and timing of patient drop-out. Recruitment over twelve months will be displayed by plotting the cumulative number of patients enrolled into our study and compared to the anticipated rate of recruitment. Graphs will also be utilized to display rates of intervention and assessment retention at each measurement time. Ninety five percent confidence intervals will be calculated and used in design considerations of a larger trial.

**2.b.** Participant retention rates in both study interventions will be described with mean, standard deviations and confidence intervals. PCBMT facilitator fidelity will be described quantitatively with the mean number of items endorsed on fidelity checklists. Also items that had lower fidelity will be described to inform future PCBMT training curriculums. Inter-rater reliability will be reported for the 25% of classes rated by an expert observer.

**2.c.** Veteran acceptability (satisfaction, perceived helpfulness, treatment retention): Total CSQ scores and scores on individual CSQ items and Intervention Acceptability items will be described with means, standard deviations and confidence intervals to understand the satisfaction and acceptability in each condition.

**2.d.i.** Patient well-being measured by PTSD severity, depression, health promoting lifestyle behaviors and recovery orientation will be described with means, standard deviations and confidence intervals at each time point by condition. To show central tendency, variation and potential trends over time, means and 95% confidence intervals will be plotted across time for each condition. Additional line plots connecting means across time will overlay the confidence intervals to help illustrate trends. We will also generate an effect size at post-treatment and at each follow-up assessment. Effect sizes will be calculated by dividing the mean difference between conditions by the pooled standard deviation. Then, 95% confidence intervals will be calculated on the effect size by using the non-central t distribution method discussed by Cummings. Graphical methods will be used to plot effects and associated confidence intervals across time which will be used to help design a larger trial. Multi-level modeling will be used to examine group by time effects for each outcome.

**Handling Missing Data.** Multiple Imputation (MI) will be used for missing data. Missing values for variables are predicted using existing values from other variables. These predicted values, called imputes, replace the

missing values resulting in a full analyzable data set. This process is performed multiple times resulting in many data sets each of which is then analyzed to produce multiple sets of results. The results are then summarized to produce a single solution. The advantage of MI over other methods, such as last observation carried forward, mean substitution, and expectation maximization, is that it preserves associations with other variables, adds variability during the imputation process and accounts for variability due to multiple imputes resulting in efficient and unbiased parameter estimates. Valid critics of MI pertain to the variables used to fill in the missing values, which may differ among analysts and lead to biased parameter estimates. To address this criticism, we plan to use recommendations from Schafer and VanBuuren as well as practical guidelines in our imputation model. Our guideline encompasses inclusion of all items from the respective measure, variables that are correlated with the analysis variable and variables that predict the missingness.

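### Self-rated PCBMT fidelity is checked only weakly: the independent observer ratings are used for a reliability coefficient from about six classes, which does not show the size or direction of any over-endorsement

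*Combined protocol and SAP*

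**What the plan says.** Two places matter.

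- **C.2.4 Measures, Aim 2.b.** The routine data are self-ratings: "PCBMT facilitators will complete a checklist of essential elements after each class". In addition, one or other of two co-investigators "will observe 25% of all classes and independently rate the fidelity assessment piloted in our earlier PCBMT study". That instrument, placed in Appendix 3, "documents observations on the delivery and enactment of treatment skills". No class is described as having two observers.
- **C.3 Analysis Plan, item 2.b.** The quantitative summary is: "PCBMT facilitator fidelity will be described quantitatively with the mean number of items endorsed on fidelity checklists". The plan then says that items with lower fidelity will be described to guide later training. It closes with "Inter-rater reliability will be reported for the 25% of classes rated by an expert observer".

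The plan does not state which raters are paired, whether they score common items, which coefficient is used, whether the unit is the item or the class, or how the observed classes are chosen. It does not commit to reporting the observer's fidelity scores as a result.

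**The concern.** Fidelity of providers and peers is a named feasibility outcome under Aim 2. The introduction gives delivery by an expert from outside the VHA as one reason why PCBMT needed refining before full-scale testing. Whether VHA staff deliver it as intended is therefore something the pilot should answer for the next trial.

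Self-completed checklists may be generous. If they are, the mean count is too high and the items needing more training are the ones least likely to show up. The observer ratings are the plan's independent evidence on this, but they are reduced to a reliability coefficient. Such a coefficient describes how closely two sets of ratings go together. It does not report the quantity of interest, which is how far self-rating exceeds observation.

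**Working it through.** **1. What is compared.** The plan gives no figure to reproduce beyond the 25% share, and no precision target. With one observer per class, a reliability figure for the observed classes has to set the observer against the facilitator or facilitators.

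**2. How many classes.** C.2.1 says "We anticipate running up three consecutive groups (PCBMT and EDU) at each of the two sites", and then "However, our timeline allows for addition groups as needed". C.2.5 gives four classes per group. The number observed is 0.25 × groups × 4:

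| Reading | Groups | Classes | Observed |
|---|---|---|---|
| Three PCBMT groups per site, two sites (main reading) | 6 | 24 | 6 |
| 30 per arm (equal allocation assumed), groups of 6 | 5 | 20 | 5 |
| One PCBMT group per site in each of four quarters | 8 | 32 | 8 |
| Three PCBMT groups in total | 3 | 12 | 3 |
| EDU classes counted as well | 12 | 48 | 12 |

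**3. Precision of a class-level coefficient.** The plan names no coefficient. As an assumption, take a one-way intraclass correlation r with k = 2 ratings on n classes:

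- F = (1 + (k-1)r)/(1-r). For r = 0.7, F = 1.7/0.3 = 5.667.
- Lower limit: L = F / F(0.975; n-1, n), then (L-1)/(L+1).
- Upper limit: U = F × F(0.975; n, n-1), then (U-1)/(U+1).

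For n = 6, L = 5.667/5.988 = 0.946, giving -0.03. U = 5.667 × 6.978 = 39.54, giving 0.95.

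| Observed classes | 95% interval at r = 0.7 | 95% interval at r = 0.8 |
|---|---|---|
| 3 | -0.48 to 0.99 | -0.28 to 0.99 |
| 5 | -0.13 to 0.96 | 0.10 to 0.98 |
| 6 | -0.03 to 0.95 | 0.20 to 0.97 |
| 8 | 0.11 to 0.93 | 0.33 to 0.96 |
| 12 | 0.26 to 0.90 | 0.46 to 0.94 |

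**4. What an item-level coefficient would show.** Assume for illustration that facilitators endorse 96% of items, the observer endorses 82%, and every disagreement is an item endorsed only by the facilitator. Agreement is 1 - 0.14 = 0.86. Chance agreement is 0.96 × 0.82 + 0.04 × 0.18 = 0.794. Kappa is (0.86 - 0.794)/(1 - 0.794) = 0.32. Exchange the two raters, so that facilitators under-endorse, and kappa is again 0.32: it carries no direction.

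Kappa also depends heavily on high endorsement. With both raters at 90% and 85% agreement (assumed), chance agreement is 0.81 + 0.01 = 0.82, and kappa is 0.03/0.18 = 0.17.

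**5. What the difference would show.** Under the same 96% and 82% assumption, with 10 items per class (assumed) and 6 classes, the difference is 14 points.

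- Items independent: variance per item 0.14 - 0.14² = 0.1204; standard error √(0.1204/60) = 0.045; 95% interval about 5 to 23 points.
- Within-class correlation 0.3 (assumed): design effect 1 + 9 × 0.3 = 3.7; standard error 0.045 × √3.7 = 0.086; interval about -3 to 31 points.

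The difference gives size and direction in interpretable units, but six classes limit its precision too.

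**The case against.** The strongest reply is that the plan already has an external check. The observer rates independently, in classes that facilitators also rate, and one observer is enough for that comparison; a second would test only consistency between observers. This stands. A reader might infer that the plan cannot show whether self-reported fidelity is true. The documents do not support that: the planned comparison is imprecise and poorly summarised, but it is a check.

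A reader might also infer that the two parties use different forms, since they are described in different words. That is not established. Appendix 3 is not in the public text, and reporting inter-rater reliability makes most sense with common items, so part of the fix may already be intended. Nor is it explicit that the checklists in the analysis plan are only the facilitators' own, although that is the natural reading.

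A third tempting step is to take the checklist's length from Table 3, which lists 6, 4, 5 and 4 content items for the four sessions, and conclude that a mean count mixes unequal scales. Nothing says the checklist follows that table, and the content is open to revision after Phase 1.

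Three further points have weight. The plan does describe low-fidelity items, so the mean count is not the only output. If both co-leaders rate separately, three ratings per class at 0.7 narrow the interval to 0.26 to 0.94 for six classes, which is still wide. And weekly supervision gives another, informal view of delivery.

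None of this supplies the missing result: the observer's own fidelity score and its difference from the self-rating.

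**Conclusion.** The point holds as a weakness in how fidelity is summarised and checked. The stated summary is most naturally read as self-rated, and the independent ratings have no stated use beyond a coefficient that is very imprecise at the likely number of classes and silent on the size and direction of bias.

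The class count is derived, not stated, and extra groups are allowed; the intervals remain wide at every count from 3 to 12. The choice of intraclass correlation, the endorsement rates, the items per class and the within-class correlation are all assumptions. The conclusion that a reliability coefficient does not report the facilitator-minus-observer difference depends on none of them.

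Severity is modest. This is a descriptive pilot aim, and no fidelity threshold, test or progression rule rests on it.

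**What to change.** Revise C.2.4 (Aim 2.b) and C.3 (item 2.b) as follows:

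1. In the classes already to be observed, facilitator and observer score the same checklist items for the same class, independently. If this is already intended, say so.
2. Express fidelity as the percentage of that session's elements delivered. This is harmless if every session has the same number of items and necessary if not.
3. Report observer-rated fidelity beside the self-rated result. The self-ratings need not be replaced, since they cover every class.
4. Report the mean facilitator-minus-observer difference and per-item percent agreement, with intervals that allow for clustering of items within classes, and state in advance that these will be wide. If a reliability coefficient is kept, name it, its unit and the rater pair.
5. Choose the observed classes so that both sites and all four sessions are represented.

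The cost is one short extra form at most, and a few sentences in the plan. No extra observers or observations are needed. The drawback is that stated fidelity may be lower.
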